#### **Study Design**

This study is a randomized, double-blind, placebo- and naproxen-controlled study designed to evaluate the efficacy and safety of fasinumab in patients with OA of the knee or hip who have a history of inadequate pain relief with acetaminophen/paracetamol and a history of intolerance to or inadequate pain relief with opioids (or are unwilling to take opioids or have lack of access to opioids).

All randomized patients in this study will participate in Year 1, which is intended to provide efficacy and safety data for OA patients exposed for up to 52 weeks to fasinumab, a non-steroidal anti-inflammatory drug (NSAID) comparator (naproxen), or placebo. At the end of the 52-week treatment period of Year 1, patients who are eligible and willing to participate in Year 2 will continue in the study for a second 52-week treatment period and will then enter the 20-week follow-up period. Note: As of 26 March 2020, all enrollment into Year 2 has been terminated due to the COVID-19 pandemic. Any patients currently enrolled in Year 2 are to remain in the study. Patients who are ineligible for Year 2, or are eligible but unwilling to enter Year 2, will enter directly into the 20-week follow-up period at the completion of Year 1.

Year 2 is intended to provide safety data for OA patients exposed to fasinumab or naproxen for up to 104 weeks (52 weeks in Year 1 and a further 52 weeks in Year 2). Note that no patients will receive placebo only in Year 2 (see Treatment Period for Year 2 below). Efficacy will be assessed during Year 2 to monitor the risk-benefit profile of fasinumab but, as Year 2 is not powered for a formal efficacy analysis, efficacy results will be summarized descriptively.

The overall study period for patients in Year 1 who do not participate in Year 2 will be up to approximately 105 weeks including screening and pre-randomization. For these patients, the study consists of a screening period of up to 30 days, a 7 to 10 day pre-randomization/washout period (7 days with a +3 day window), a 52-week treatment period, a 20-week follow-up period, and an end of study phone contact at 52 weeks following the last subcutaneous (SC) dose of study drug. Eligible patients who choose to participate in Year 2 will receive treatment for a total of 104 weeks and will then enter a 20-week follow-up period, followed by the final phone call approximately 52 weeks after the last dose of SC study drug.

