Note: As of 17August 2020, all patients on treatment have been permanently discontinued from study drug and will complete the End of Treatment visit. This impacts only patients in the Year 2 treatment period as treatment in Year 1 has ended. All patients will be encouraged to complete all remaining study visits and procedures in the follow-up period and the end of study phone call.

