Note: Any Year 1 patient attending their week 52 visit on or after 26 March 2020 will no longer have the option to enroll into Year 2.

- 1. Completed the treatment period of Year 1
- 2. Did not permanently discontinue study drug during Year 1
- 3. Received no less than 10 of the 13 planned doses of SC study drug during the treatment period of Year 1
- 4. Provide informed consent for Year 2
- 5. Willing to continue to maintain current activity and exercise levels throughout Year 2
- 6. Willing and able to comply with clinic visits and study-related procedures and willing to provide follow-up information related to any JR surgery that occurs within the period of time covered by their intended participation in the study

#### 6.2.4. Exclusion Criteria for Year 2

Women of childbearing potential who are unwilling to continue to practice highly effective contraception during the study, and for at least 20 weeks after the last dose. Highly effective contraceptive measures include stable use of combined (estrogen and progestogen-containing) hormonal contraception (oral, intravaginal, transdermal) or progestogen-only hormonal contraception (oral, injectable, implantable) associated with inhibition of ovulation initiated 2 or more menstrual cycles prior to screening; intrauterine device (IUD); intrauterine hormone-releasing system (IUS); bilateral tubal ligation; vasectomized partner; and or sexual abstinence†‡.

† Sexual abstinence is considered a highly effective method only if defined as refraining from heterosexual intercourse during the entire period of risk associated with the study

treatments. The reliability of sexual abstinence needs to be evaluated in relation to the duration of the clinical trial and the preferred and usual lifestyle of the subject.

‡ Periodic abstinence (calendar, symptothermal, and post-ovulation methods), withdrawal (coitus interruptus), spermicides only, and lactational amenorrhea method (LAM) are not acceptable methods of contraception. Female condom and male condom should not be used together.

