#### **3.1. The Full Analysis Set (FAS)**

The FAS includes all randomized patients excluding patients affected by the urgent safety measure (i.e. patients randomized to the 3 mg Q4W or 6 mg Q8W doses) and is based on the treatment allocated (as randomized). Efficacy and patient reported outcome endpoints for Year 1 will be analyzed using the FAS including patients randomized to fasinumab 1 mg Q4W, fasinumab 1 mg Q8W, naproxen and placebo. For the analyses of fasinumab 1 mg Q8W group comparing to the control groups, only patients concurrently randomized (i.e. after Protocol R475-OA-1611 Amendment 5 Global was implemented) will be included.

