#### **3.4. The Safety Analysis Sets (SAF)**

The Year 1 safety analysis set (SAF – Year 1) includes all randomized patients from the FAS who received any study drug; it is based on the treatment received (as treated). Treatment compliance/administration and all clinical safety variables for Year 1 will be analyzed using the

SAF – Year 1 including patients randomized to fasinumab 1 mg Q4W, fasinumab 1 mg Q8W, naproxen, and placebo.

The Year 2 safety analysis set (SAF – Year 2) includes all patients who received at least 1 dose of the Year 2 study drug; it is based on the treatment received during Year 2 (as treated). Treatment compliance/administration, all clinical efficacy and safety variables and all patient reported outcomes from Year 2 will be analyzed using the SAF – Year 2.

The following rules will be used to define the actual treatment a patient received:

- Patients randomized to either the placebo or naproxen arm who receive at least one dose of active fasinumab during Year X will be considered as treated with fasinumab 1 mg Q8W and classified in the fasinumab 1 mg Q8W treatment arm for the purpose of analysis using the SAF – Year X, where X = 1 or 2.
- Patients randomized to the placebo arm who have not received any active fasinumab injections but were ever dispensed active naproxen during Year 1 will be considered as treated with naproxen and classified in the naproxen treatment arm for the purpose of analysis using the SAF – Year 1.
- For patients randomized to either the fasinumab 1 mg Q8W or Q4W arms, as treated is defined to be as randomized and they will be classified in the treatment arm they were randomized to for the purpose of the analysis using the SAF – Year X, where X = 1 or 2, with the following exceptions:
  - In Year 1, if a patient receives no doses of active naproxen or fasinumab, then the patient will be considered as treated with placebo and classified in the placebo treatment arm for the purpose of analysis using the SAF – Year 1.
  - In Year 1, if a patient receives no doses of fasinumab but were ever dispensed any active dose of naproxen, then the patient will be considered as treated with naproxen and classified in the naproxen treatment arm for the purpose of analysis using the SAF – Year 1.
  - In Year 2, if a patient receives no doses of fasinumab, then the patient will be considered as treated with naproxen prn and classified in the naproxen prn treatment arm for the purpose of analysis using the SAF – Year 2.

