## 5. STATISTICAL METHODS

For continuous variables, descriptive statistics will include the following: the number of patients reflected in the calculation (n), mean, median, standard deviation, minimum & maximum and 1st & 3rd quartiles (Q1 & Q3).

For categorical or ordinal data, frequencies and percentages will be displayed for each category.

**Period of observation** – Unless otherwise stated, analysis of all safety variables captured at multiple visits will be analyzed by the following observations periods:

- The Pre-Treatment Period is defined as the time from signing the ICF to before the first dose of study drug in Year 1.
- The Year 1 On-Treatment Period is defined as the day from first dose of Year 1 study drug through the day of last Year 1 SC dose + 4 weeks for those patients not proceeding into Year 2, or up to the first dose of Year 2 study drug for those patients proceeding into Year 2. Summaries for the Year 1 On-Treatment Period will be based on the SAF – Year 1.
- The Year 1 Post-Treatment Period is defined from the end of the Year 1 On-Treatment Period to the Week 72/Early Termination Visit for those patients not proceeding into Year 2. Summaries for the Year 1 Post-Treatment Period will be based on the SAF – Year 1.
- The Year 2 On-Treatment Period is defined as the day from first dose of Year 2 study drug through the day of last Year 2 SC dose + 4 weeks for those patients proceeding into Year 2. Summaries for the Year 2 On-Treatment Period will be based on the SAF – Year 2.
- The Year 1 and 2 On-Treatment Period is defined as day from first dose of Year 1 study drug through the day of last SC dose + 4 weeks. Summaries for the Year 1 and 2 On-Treatment Period will be based on both the SAF – Year 1 and SAF-Year 2.
- The Year 2 Post-Treatment Period is defined from the end of the Year 2 On-Treatment Period to the Week 124E/Early Termination E Visit for those patients proceeding into Year 2. Summaries for the Year 2 Post-Treatment Period will be based on the SAF – Year 2.

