### 5.8.1. Adverse Events

The verbatim text, the preferred term (PT), and the primary system organ class (SOC) will be displayed in subject listings. Summaries that include frequencies and proportions of patients reporting AEs will include the PTs and the SOCs.

**Pre-treatment AEs** are defined as AEs that developed or worsened during the Pre-Treatment Period.

**Treatment-emergent AEs (TEAEs)** are defined as AEs that developed or worsened during the On-Treatment Periods.

**Post-treatment AEs** are defined as AEs that developed or worsened more than 4 weeks after the last dose of SC study drug.

The focus of adverse event reporting in the clinical study report will be on TEAEs.

For details on handling missing data and partial dates, see Section 6.4.

Summaries of all TEAEs in each treatment group will include:

- Overview of TEAEs, summarizing number of events and number and percentage of patients within the specified category:
  - Total number of TEAEs
  - Total number of serious TEAEs
  - Total number of treatment-emergent AESIs
  - Patients with any TEAEs
  - Patients with any serious TEAEs
  - Patients with any treatment-emergent AESIs
  - Patients with any TEAEs leading to permanent discontinuation from study drug

- Patients with any TEAEs leading to withdrawal from the study
- Patients with any TEAEs leading to death
- TEAEs by SOC and PT
  - All TEAEs
  - TEAEs by severity: mild, moderate or severe
  - TEAEs resulting in permanent study treatment discontinuation
- Study-Drug related TEAEs by SOC and PT
  - All TEAEs
- TEAEs by PT
  - All TEAEs
  - TEAEs resulting in permanent study treatment discontinuation
- Post-treatment AEs by SOC and PT
  - All post-treatment AEs
  - Post-treatment AEs by severity: mild, moderate or severe
- All Serious TEAEs by SOC and PT
- Post-treatment Serious AEs by SOC and PT
- All serious AEs by SOC and PT
- All non-serious TEAEs by SOC and PT
- Post-treatment non-serious AEs by SOC and PT
- All non-serious AEs by SOC and PT
- All AEs by SOC and PT
  - All AEs
  - All AEs by severity: mild, moderate or severe
- Deaths

Counts will be provided according to treatment group for each PT within each SOC. Percentages will be calculated using the number of patients in each treatment group using the respective SAF.

Primary SOC's will be sorted by descending frequency of the 'Fasinumab 1 mg SC Q4W' treatment group. Within each primary SOC, PTs will be sorted by decreasing frequency of investigational product.

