A second type of table with counts of each primary SOC in decreasing order of frequency will be provided. A third type of table with counts of each PT in decreasing order of frequency will also be provided.

The above TEAE analyses will be performed for the Year 1 On-Treatment Period, Year 2 On-Treatment Period, Year 1 and 2 On-Treatment Period, Year 1 Post-Treatment Period and Year 2 Post-Treatment Period using the corresponding analyses sets specified in Section 5.

The following listings will be included:

- AEs leading to death
- TEAEs leading to permanent discontinuation from study drug (not applicable to post-treatment AEs)
- TEAEs leading to withdrawal from study
- Patients with Serious TEAEs
- AESIs
- Deaths
- All Cause Joint Replacements
- Pre-treatment AEs
- Post-treatment AEs

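### Year 2 and combined-period adverse event tables give crude percentages only, so Q8W, which has no patients from before Amendment 5, can be compared over unequal time at risk

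*SAP*

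**What the plan says.** **How events are summarised.** SAP 5.8.1 sets the denominator: "Percentages will be calculated using the number of patients in each treatment group using the respective SAF". The same tables are repeated by period: "The above TEAE analyses will be performed for the Year 1 On-Treatment Period, Year 2 On-Treatment Period, Year 1 and 2 On-Treatment Period". SAP 5.8.2 reports AESIs as plain incidence by arm. Exposure and length of observation are described separately (SAP 5.6.2 and 5.6.3) and enter no event rate. Neither document plans an adverse event rate per patient-year.

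**Which patients.** For the combined period SAP 5 says: "Summaries for the Year 1 and 2 On-Treatment Period will be based on both the SAF – Year 1 and SAF-Year 2". Protocol 10.4.4 names SAF - Year 1 only. SAP 3.4 defines that set without a concurrency condition: "The Year 1 safety analysis set (SAF – Year 1) includes all randomized patients from the FAS who received any study drug". For Q8W efficacy comparisons, SAP 3.1 does impose one: "only patients concurrently randomized (i.e. after Protocol R475-OA-1611 Amendment 5 Global was implemented) will be included". SAP 3.2 repeats it for the mFAS.

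**Calendar cut-offs.** The Protocol Synopsis (Study Design) says "As of 26 March 2020, all enrollment into Year 2 has been terminated due to the COVID-19 pandemic" and "As of 17August 2020, all patients on treatment have been permanently discontinued from study drug". Protocol 6.2.3 applies the first date to individuals: "Any Year 1 patient attending their week 52 visit on or after 26 March 2020 will no longer have the option to enroll".

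**What is already adjusted for follow-up.** SAP 5.8.7 plans Kaplan-Meier summaries of time to first adjudicated arthropathy (AA) and destructive arthropathy (DA), with Cox models of each arm against placebo, and Kaplan-Meier curves of time to joint replacement (JR).

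**The concern.** On SAF - Year 1, the combined-period percentage puts patients planned for 52 weeks and patients treated for up to 104 weeks into one denominator. On SAF - Year 2 that mix does not arise, but the length of Year 2 still varies with entry date because dosing ended on one calendar day.

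The date at which a patient could enter Year 2, and the dosing time left after entry, follow from the randomization date. Q8W was opened only under Amendment 5, so its randomization dates are distributed differently from those of the other arms. A crude percentage for Q8W can then differ from another arm's at the same underlying event rate. The efficacy analyses guard against non-concurrent comparison; the safety analyses do not.

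Secondary objective 5 is safety against naproxen for up to 104 weeks, and Year 1 tables cannot answer it. For TEAEs, serious TEAEs, TEAEs leading to discontinuation, sympathetic nervous system AESIs and peripheral sensory AESIs, the Year 2 and combined tables are the planned evidence, and they carry no allowance for follow-up.

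**Working it through.** **1. Planned arm sizes (Protocol 5.1.3).** Patients before plus after Amendment 5:

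- Q4W: 240 + 600 = 840
- Naproxen: 240 + 600 = 840
- Placebo: 80 + 200 = 280
- Q8W: 0 + 600 = 600

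The sum is 2560, which reproduces the protocol's total. The share randomized before Amendment 5 is 240/840 = 240/840 = 80/280 = 28.6% in three arms and 0/600 = 0% in Q8W.

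**2. What the dates imply (nominal study days, Protocol Tables 1 and 2).** Week 52 is day 365 and the last Year 2 injection, week 100E, is day 701.

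- 26 March 2020 minus 364 days = 28 March 2019. Patients randomized from about then on could not enter Year 2.
- 17 August 2020 minus 700 days = 17 September 2018. Patients randomized after about then would not reach the week 100E injection before dosing stopped.
- 25 March 2020 to 17 August 2020 = 145 days = 20.7 weeks. This is the most Year 2 dosing time open to a patient entering on the last possible day.

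**3. Effect on a crude percentage when all arms have the same hazard.** For a group of size n with hazard λ and time t, the crude risk is 1 − exp(−λt). An arm's percentage is the n-weighted average over its groups. The follow-up times, Year 2 entry fractions and hazards below are assumptions; the documents give none of them by arm.

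Example with λ = 0.02 per year, pre-Amendment 5 patients followed 2 years and later patients 1 year:

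- Q4W: (240/840) × (1 − e^−0.04) + (600/840) × (1 − e^−0.02) = 2.53%
- Q8W: 1 − e^−0.02 = 1.98%
- Ratio Q8W/Q4W = 0.781

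| Assumed mix | Mean years, Q4W / Q8W | Q8W/Q4W, λ = 0.02 | Q8W/Q4W, λ = 0.10 |
|---|---|---|---|
| Extreme: pre 2 y, post 1 y | 1.286 / 1.000 | 0.781 | 0.795 |
| Extreme: pre 1 y, post 2 y | 1.714 / 2.000 | 1.165 | 1.157 |
| Pre: 50% enter for 52 weeks; post: 30% for 26 weeks | 1.250 / 1.150 | 0.921 | 0.927 |
| Pre: none enter; post: 40% for 39 weeks | 1.214 / 1.300 | 1.070 | 1.066 |
| Same entry and exposure in both cohorts | 1.262 / 1.262 | 1.000 | 1.000 |

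In every row the crude Q4W/naproxen ratio is 1.0, because those arms have the same planned pre/post mix. In every row the rate per patient-year is equal across arms by construction, and Q8W against post-Amendment 5 patients only also gives 1.0.

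**4. Limit of the rate remedy.** Suppose 20% of one arm and 40% of another enter Year 2 for 0.7 years, with a hazard of 0.20 in Year 1 and 0.05 in Year 2 in both (all assumed).

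- Risk without Year 2: 1 − e^−0.20 = 18.13%. Risk with Year 2: 1 − e^−0.235 = 20.94%.
- Crude: 0.8 × 18.13 + 0.2 × 20.94 = 18.69%, against 0.6 × 18.13 + 0.4 × 20.94 = 19.25%. Ratio 1.03.
- Years to first event or end of period: 0.906 + 0.2 × 0.563 = 1.019, against 0.906 + 0.4 × 0.563 = 1.132. Here 0.906 = (1 − e^−0.20)/0.20 and 0.563 = e^−0.20 × (1 − e^−0.035)/0.05.
- Rates: 18.69/1.019 = 18.3 and 19.25/1.132 = 17.0 per 100 patient-years. Ratio 0.93.

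A single pooled rate can therefore mislead when the hazard changes between years.

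**The case against.** The strongest case against the point has five parts.

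- **The cut-offs do not unbalance every comparison.** A reader might infer that they distort all between-arm comparisons, including Q4W against naproxen. The documents do not support that. These arms and placebo have the same planned accrual mix, so the dates act on them equally in expectation. Unequal time there would need differential discontinuation or selective Year 2 entry. Entry does require no permanent discontinuation and at least 10 of 13 injections (Protocol 6.2.3), but no figures by arm are given.
- **Not all AESIs lack follow-up adjustment.** A reader might infer that they do. AA, DA and JR have time-to-event summaries; only sympathetic and peripheral sensory events rest on incidence alone.
- **SAF - Year 2 removes the 52/104-week mix.** This stands for that half of the SAP's combined-period tables. It leaves the variable length of Year 2, and the mix remains on SAF - Year 1, the only set protocol 10.4.4 names.
- **Mitigation exists.** Year 1 tables compare arms over the same planned 52 weeks, the summaries are descriptive, and exposure is tabulated. A reader can see unequal exposure but cannot derive first-event rates by event category from these tables.
- **Timing.** The SAP follows Amendment 8 and the dosing stop came with Amendment 9, so the SAP could not have reflected it. Protocol 10.4.4 as amended still adds no adjustment.

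The caution about exposure-adjusted rates also stands: they equalise only under a constant hazard, and Year 2 entrants are a selected group.

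**Conclusion.** The point holds for Q8W comparisons in the Year 2 and combined on-treatment tables, for TEAEs, serious TEAEs, TEAEs leading to discontinuation, and sympathetic and peripheral sensory AESIs. The plan has neither a concurrent-control rule nor a follow-up adjustment there.

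Direction and size cannot be determined. The implementation dates of Amendments 5 and 6 and Year 2 entry by arm are not given, and patients from before Amendment 5 may have had more or less access to Year 2 than later ones. Under equal constant hazards and full Year 1 follow-up, the assumed extreme mixes on SAF - Year 1 give crude Q8W/Q4W ratios of about 0.78 to 1.17. The two milder unequal mixes give about 0.92 to 1.07. These are illustrations, not estimates of what the trial will show.

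The point does not extend to a calendar-driven bias between Q4W, naproxen and placebo. It is an inexpensive improvement to the safety reporting and leaves the efficacy conclusions untouched.

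**What to change.** 1. Keep the crude percentages.
2. For Q8W comparisons in the Year 2 and combined periods, use only patients randomized after Amendment 5 was implemented, as the efficacy analyses already do.
3. For the five event categories above, add a follow-up-adjusted summary by arm: either Kaplan-Meier cumulative incidence of first event, or exposure-adjusted incidence per 100 patient-years with 95% CI. Give the difference of each fasinumab dose from naproxen.
4. If rates are used, state the constant-hazard assumption and show Year 1 and Year 2 rates separately.
5. Reconcile SAP 5 with protocol 10.4.4 on the analysis set for the combined period, and label each table with its set.

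**Cost.** SAP wording and a few extra tables from dates already collected. Q8W comparisons lose some precision. With planned numbers and equal event proportions, the standard error of a risk difference on SAF - Year 1 grows by √[(1/600 + 1/600)/(1/600 + 1/840)] = 1.08 against naproxen and √[(1/600 + 1/200)/(1/600 + 1/280)] = 1.13 against placebo. The full-arm columns can stay alongside.

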### **5.8.2. Analysis of Adverse Events of Special Interest**

Adverse events of special interest (AESI) include adjudicated arthropathies, AEs confirmed as SNS dysfunction and peripheral neurosensory events, and joint replacements meeting pre-specified AESI criteria. AESIs will be flagged in the database using predefined tick boxes to denote the events.

Summaries of AESI incidence by treatment group will include:

- Incidence of adjudicated arthropathy events
- Incidence of adjudicated arthropathies that meet destructive arthropathy criteria
- Incidence of joint replacements AESI events
- Incidence of sympathetic nervous system dysfunction AESI events
- Incidence of peripheral neurosensory AESI events

